#### **9.5.4 Appropriateness of Measurements**

All safety and efficacy variables, as well as the methods to measure them, are standard variables/methods in clinical trials and/or clinical practice and are widely used and generally recognized as reliable, accurate and relevant.

The HAQ-DI [Cole et al., 2006], SHAQ [Johnson et al., 2005; Steen and Medsger, 1997], UCLA SCTC GIT 2.0 [Khanna et al., 2009], SSPRO-18 [Man et al., 2017], Raynaud's Condition Score Diary [Merkel et al., 2003], SScQoL [Sierakowska et al., 2019], SF-12 [Andrade et al., 2007; Khanna et al., 2010] and FACIT-F [Harel et al., 2012; Strickland et al., 2012] have been validated for use in subjects with SSc.

#### **9.5.5 Trial Procedures**

Trial procedures and timing are detailed in the Schedule of Assessments (Section 2.1).

Select visits may be completed at an alternative remote location, e.g., a subject's home, by a visiting home healthcare professional and will be based on local availability and as allowable based on local laws and regulations. Remote locations will be discussed during the consent process per subject's preference and as approved by the Investigator. Site Investigators will have direct awareness and oversight of remote subject visits.

The end of the trial is defined as the date of the last visit of the last subject undergoing the trial.

##### **9.5.5.1 Effect of a Pandemic on Trial Procedures**

In situations due to coronavirus disease 2019 (COVID-19) where trial subjects cannot attend scheduled clinic visits, the following modifications may be considered:

- For efficacy assessments, a home visit or a subject-collected FVC may be used. For patient-reported outcomes or other questionnaires, a telephone visit, virtual visit or home visit may be used to collect information.
- For safety assessments, a local laboratory or a home visit may be used to collect laboratory-related assessments to monitor safety and results will be communicated to the Medical Monitor. A telephone visit, virtual visit or home visit may be used to collect

information on AEs and drug compliance. Investigators may also consider shipping fipaxalparant (HZN-825) to a subject's home via appropriate courier, if necessary.

- If data are captured in an irregular manner (e.g., patient-reported outcomes via telephone or FVC in-home) this should be captured via source documentation. If possible, these protocol modifications should be discussed with the Sponsor and contract research organization prior to implementation, but deviations to immediately address subject safety are possible per the Investigator's discretion.

## **9.6 Statistical Methods and Determination of Sample Size**

### **9.6.1 Endpoints**

Two types of Baseline are defined:

- Trial Baseline, defined as the latest measurement prior to the first dose of fipaxalparant (HZN-825) in this extension trial
- Fipaxalparant (HZN-825) Baseline, defined as the latest measurement prior to the first dose of the trial drug in Trial HZNP-HZN-825-301.

#### **9.6.1.1 Primary Efficacy Endpoint**

The primary endpoint is the change from both Baselines in FVC % predicted at Week 52.

#### **9.6.1.2 Exploratory Efficacy Endpoints**

1. Change from both Baselines in the mRSS at Week 52.
2. Proportion of subjects responding to treatment based on CRISS 25 at Week 52.
3. Change from both Baselines in HAQ-DI at Week 52.
4. Change from both Baselines in CGA at Week 52.
5. Change from both Baselines in PTGA at Week 52.
6. Change from both Baselines in the Physical Effects subscale of the SSPRO-18 at Week 52.
7. Change from both Baselines in the Physical Limitations subscale of the SSPRO-18 at Week 52.
8. Proportion of subjects with an mRSS decrease of  $\geq 5$  points and 25% from both Baselines at Week 52.
9. Responder rate (defined as ACR-CRISS [predicted probability] of at least 0.6) at Week 52.
10. Change from both Baselines in the SSPRO-18 at Week 52.
11. Change from both Baselines in each scale of the UCLA SCTC GIT 2.0 and the total GIT score at Week 52.
12. Change from both Baselines in Raynaud's phenomenon using the Raynaud's Assessment at Week 52.
13. Change from both Baselines in the SHAQ at Week 52.

14. Change from both Baselines in SScQoL scores at Week 52.
15. Change from both Baselines in SF-12 scores at Week 52.
16. Change from both Baselines in pain and pain component scale scores at Week 52.
17. Change from both Baselines in the FACIT-F score at Week 52.
18. Change from both Baselines in lung fibrosis based on HRCT at Week 52.
19. Change from both Baselines in DLCO at Week 52.
20. Change from both Baselines in serum and plasma biomarkers associated with LPAR1 pathway, inflammation and/or fibrosis at [REDACTED]
21. Change from both Baselines in [REDACTED]  
[REDACTED]

#### **9.6.1.3 Safety and Tolerability Endpoints**

1. Incidence of TEAEs and the AESI [REDACTED]
2. Concomitant medication use.
3. Vital signs.
4. 12-lead ECGs.
5. Clinical safety laboratory evaluations.

#### **9.6.1.4 Pharmacokinetic Endpoint**

1. Pre- and post-dose concentrations of fipaxalparant (HZN-825).

### **9.6.2 Analysis Sets**

Four analysis sets will be defined for this trial.

- The full analysis set (FAS) will include all subjects who were enrolled (i.e., signed the ICF) and who received at least 1 dose or partial dose of fipaxalparant (HZN-825) in this extension trial. This will be the analysis set used for efficacy data analyses and subjects will be analyzed according to the treatment group to which they were randomized in the previous trial, and combined into an ‘overall’ group.
- The safety analysis set will include all subjects who received at least 1 dose or partial dose of fipaxalparant (HZN-825) in this extension trial. Subjects in this analysis set will be analyzed according to the group determined by the treatment that the subject received in the previous trial and overall, and combined into an ‘overall’ group.
- The PK analysis set will include all subjects who received at least 1 dose or partial dose of fipaxalparant (HZN-825) and had at least 1 PK sample post fipaxalparant (HZN-825) treatment in this extension trial.
- The Per-Protocol (PP) analysis set will consist of all subjects in the FAS with no major protocol violations. The PP analysis set will be used, as needed, for supportive analysis of the primary endpoint and potentially other key endpoints. Subjects in this analysis set

will be analyzed according to the treatment group to which they were randomized in the previous trial, and combined into an ‘overall’ group.

### 9.6.3 Efficacy Endpoint Analysis

All efficacy endpoints will be summarized for the FAS using descriptive statistics, presented by the treatment group subjects were randomly assigned to in HZNP-HZN-825-301 and overall.

A mixed model for repeated measures (MMRM) will be fit to the data *for descriptive purposes* using observed change in FVC % predicted values from all planned post-Trial Baseline assessments (Weeks 16, 28, 40 and 52). The model will include the fixed covariates of: factors used for stratifying randomization (use of mycophenolate mofetil [yes/no] and presence of ILD [yes/no]), treatment the subject received in the previous trial, treatment by Visit Week and Visit Week. The Trial Baseline value will be used as a continuous covariate. An unstructured covariance matrix will be used for the primary analysis; if the model does not converge, other covariance matrices will be considered. The least squares mean (LS mean) difference in change from Trial Baseline to Week 52 from MMRM will be estimated from this model. For subjects with missing data at 1 or more time points, the available data will be included in the analysis.

Exploratory endpoints will be summarized at each time point. Change from Baseline will be evaluated separately for each of the defined Baselines.

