2. On Day 1 (Baseline), subjects will receive the first dose of fipaxalparant (HZN-825) in this extension trial in the clinic. All Day 1 assessments should be performed before the first dose of trial drug is administered in the clinic.
3. Performed as part of the Week 52 Visit of HZNP-HZN-825-301; if applicable, the result will be considered a Trial Baseline value for this extension trial.
4. Except when strictly unavoidable, the same person should perform the assessment at each evaluation during the trial. The mRSS assessment should be performed by a qualified Investigator (or designee).
5. The lung HRCT scan should be performed within ±2 weeks of the Week 52/PD Visit.
6. DLCO can be assessed within ±2-weeks of the Week 28 and Week 52/PD Visits.
7. Daily electronic diaries will be completed for 4 weeks starting on Day 1, 4 weeks starting at the Week 22 Visit and 4 weeks starting at the Week 46 Visit.
8. Perform for WOCBP. Serum pregnancy test at [REDACTED] (or as needed). Urine pregnancy tests should also be done every 4 weeks after Day 1, which includes both in-clinic testing at scheduled visits prior to dosing [REDACTED] and at home (also a ±7-day window) by the subject and reported to the site [REDACTED]. A urine pregnancy test will also be done at the Safety Follow-up Visit.
9. A complete physical examination, including but not limited to cardiac, pulmonary, neurologic and skin assessments, as well as directed rheumatology assessments [REDACTED]
10. Vital signs (blood pressure, heart rate, respiratory rate, temperature) will be measured at each visit.
11. Additional electrocardiograms or echocardiograms will be conducted, if clinically indicated. A standard transthoracic echocardiogram will be conducted on Day 1. However, an echocardiogram that has been performed during HZNP-HZN-825-301 and within the 3 months prior to HZNP-HZN-825-302 Day 1 can serve as the Trial Baseline echocardiogram if the subject has been clinically stable.
12. See Section 9.5.3.8 for details.
13. ESR must be processed within 1 hour of the blood draw.

14. Autoantibodies include anti-centromere antibody, anti-RNA polymerase antibody, anti-topoisomerase 1 and anti-U1 small nuclear ribonucleoprotein.
15. PK samples will be collected at each of the following visits: Day 1 (pre-dose), Week 4 (pre-dose and 2 to 4 hours post-dose) and Weeks 16, 28 and 40 (pre-dose). Note: all pre-dose samples will be collected prior to any fipaxalparant (HZN-825) administration for the day.

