## 9 INVESTIGATIONAL PLAN

### 9.1 Overall Trial Design and Plan

This trial will be conducted at up to 135 sites globally.

[figure not shown]
This is an open-label, repeat-dose, multicenter extension trial of HZNP-HZN-825-301. Subjects who complete the double-blind Treatment Period (Week 52) in Trial HZNP-HZN-825-301 will be eligible to enter this 52-week extension trial. Subjects entering this extension trial will complete the Week 52 Visit activities in HZNP-HZN-825-301 and will not complete the Safety Follow-up Visit 4 weeks after the last dose of trial drug in HZNP-HZN-825-301. All HZNP-HZN-825-301 Week 52 assessments should be performed before the first dose of the extension trial drug is administered.

On Day 1 (Week 52 Visit of HZNP-HZN-825-301), subjects will receive their first dose of fipaxalparant (HZN-825) in this extension trial at the clinic and will participate in trial visits at Week 4 and every 6 weeks thereafter until Week 52. The Week 52 Visit activities in HZNP-HZN-825-301 will serve as Trial Baseline for this extension trial.

If a subject prematurely discontinues trial drug, he/she will be asked to remain in the trial, participating in the scheduled trial visits through Week 52. If a subject prematurely discontinues trial drug and does not wish to continue in the trial, he/she will return for a clinic visit and undergo the Week 52 assessments. Subjects will participate in a Safety Follow-up Visit 4 weeks after the last dose of fipaxalparant (HZN-825).

An overview of the trial design is presented in [Figure 9.1](#) and details of trial activities are provided in [Section 2.1, Schedule of Assessments](#).

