#### **9.3.3.1 Removal of Subjects from Treatment**

The primary reason for discontinuation from trial drug should be recorded on the eCRF using one of the following categories:

- AE or clinically significant laboratory/electrocardiogram (ECG) abnormality. The subject experiences an AE or clinically significant laboratory/ECG abnormality that imposes an unacceptable risk to the subject's health, or the subject is unwilling to continue receiving treatment because of an AE or clinically significant laboratory/ECG abnormality. Subjects who discontinue trial drug due to an AE or clinically significant laboratory/ECG abnormality will remain in the trial unless they withdraw from the trial for another reason. In such cases, if the situation is not an immediate emergency, the Investigator should contact the trial Medical Monitor.
- Drug-induced liver injury. Trial drug discontinuation should be considered if:
  - alanine aminotransferase (ALT) or aspartate aminotransferase (AST)  $>8 \times$  upper limit of normal (ULN)
  - ALT or AST  $>5 \times$  ULN for more than 2 weeks

- ALT or AST  $>3 \times$  ULN and (total bilirubin [TBL]  $>2 \times$  ULN or international normalized ratio  $>1.5$ )
- ALT or AST  $>3 \times$  ULN with the appearance of fatigue, nausea, vomiting, right upper quadrant pain or tenderness, fever, rash and/or eosinophilia ( $>5\%$ )

Subjects who have ALT or AST levels  $>3 \times$  ULN confirmed in a repeat test need to undergo close observation as prescribed by the [FDA guidance](#) on drug-induced liver injury (refer to Appendix 17.15). Close observation includes repeating liver enzyme and serum bilirubin tests 2 or 3 times weekly. Frequency of retesting can decrease to once a week or less if abnormalities stabilize and the subject is asymptomatic. The decision to rechallenge the subject is to be discussed and agreed upon by the Investigator, and Amgen Medical Monitor.

- Lack of efficacy. Discontinuation of trial drug due to lack of efficacy is at the discretion of the Investigator or subject and may occur if the Investigator determines that trial drug administration is not benefitting the subject. Subjects who discontinue trial drug due to lack of efficacy will remain in the trial for scheduled safety and efficacy assessments through Week 52 unless they also withdraw from the trial for another reason.

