#### **9.1 Primary Efficacy Endpoint Analysis**

The primary efficacy endpoint will be the change from both Baselines (Trial Baseline and HZN-825 Baseline) in FVC% predicted at Week 52.

A mixed model for repeated measures (MMRM) will be fit to the data for descriptive purposes using observed change in FVC % predicted values from all planned post-Trial Baseline assessments (Weeks 16, 28, 40 and 52). The model will include the fixed covariates factors used for stratifying randomization (use of mycophenolate mofetil [yes/no] and presence of ILD [yes/no]) in the previous trial, the treatment received in the previous trial, treatment by Visit Week and Visit Week. The Trial Baseline value will be used as a continuous covariate. An unstructured covariance matrix will be used for the primary

analysis; if the model does not converge, other covariance matrices or descriptive statistics will be considered. The least squares mean (LS mean) difference in change from Trial Baseline to Week 52 in MMRM will be estimated from this model. For subjects with missing data at 1 or more time points, the available data will be included in the analysis. A similar process for the FVC % predicted for the change from HZN-825 Baseline will also be performed.

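### SAP 9.1 does not write out the FVC model for change from HZN-825 Baseline; it should fix the covariate and make the 301 Week 52 change a response

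*Protocol*

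**What the plan says.** Protocol 9.6.1.1 sets a two-part endpoint: "The primary endpoint is the change from both Baselines in FVC % predicted at Week 52".

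Protocol 9.6.3 specifies one MMRM, for change from Trial Baseline, "using observed change in FVC % predicted values from all planned post-Trial Baseline assessments (Weeks 16, 28, 40 and 52". On the covariate it says "The Trial Baseline value will be used as a continuous covariate", and on the contrast "The least squares mean (LS mean) difference in change from Trial Baseline to Week 52 from MMRM will be estimated from this model". Trial Baseline is the last visit of the parent trial: "The Week 52 Visit activities in HZNP-HZN-825-301 will serve as Trial Baseline for this extension trial" (Protocol 9.1). Spirometry on Day 1 is therefore the 301 Week 52 test, and footnote 3 of the Schedule of Assessments confirms that "the result will be considered a Trial Baseline value for this extension trial". The next scheduled spirometry is at 302 Week 16.

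The protocol gives no MMRM for change from HZN-825 Baseline. SAP 9.1 repeats the Trial Baseline model and adds one sentence: "A similar process for the FVC % predicted for the change from HZN-825 Baseline will also be performed". It restates neither the response visits nor the covariate. SAP 7 rules out imputation except for exploratory purposes, and SAP 9.2 sends the exploratory change endpoints through the same analysis.

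**The concern.** For change from Trial Baseline, the 301 Week 52 FVC is the baseline and belongs on the covariate side. For change from HZN-825 Baseline, the same measurement is an outcome at the one-year point. It is scheduled for every entrant and is the last value before any loss during 302. A process copied from the Trial Baseline model does not use it as an outcome.

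Two readings of the SAP sentence give different estimates:

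- **A: HZN-825 Baseline becomes the covariate.** The 301 Week 52 value is then not in the model. A full analysis set subject with no FVC after Day 1 contributes nothing, although a year-1 change is on file.
- **B: Trial Baseline stays as covariate.** Prior arms are then compared at equal 301 Week 52 FVC, which removes part of the year-1 difference that this endpoint is meant to contain.

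At stake is the estimate that serves the aim, in Protocol 7.2, of assessing durability of response over up to 24 months.

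**Working it through.** The documents give no sample size, SD or dropout rate, so there is no stated figure to reproduce. All numerical inputs below are assumptions.

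**1. Dropout under reading A.** Assumptions: true year-1 change mean -3 (SD 6), year-2 change mean -1 (SD 4), measurement SD 3, so a true two-year change of about -4. The log odds of leaving rise by 0.5 or 1.0 per SD of observed year-1 decline. The check was a simulation of 400,000 subjects per scenario in one group, with unstructured maximum likelihood under monotone dropout.

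If leavers have no FVC after Day 1, the fit describes stayers only:

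bias = share leaving × (stayers' minus leavers' mean two-year change).

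Two-year change follows observed year-1 change with slope (6² + 3²)/(6² + 2×3²) = 45/54 = 0.833, because the two changes share the true year-1 change and the HZN-825 Baseline error. With 10% leaving, log odds 1.0 and a simulated year-1 gap of 6.64 points: 0.10 × 6.64 × 0.833 = 0.55, as simulated.

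| Pattern of leaving | 5% leave | 10% leave |
|---|---|---|
| Before Week 16, no later FVC | +0.15 to +0.29 | +0.30 to +0.55 |
| About Week 8, discontinuation FVC mapped to Week 16 | +0.02 to +0.03 | +0.05 to +0.07 |
| After the Week 16 FVC | +0.01 to +0.03 | +0.03 to +0.06 |

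Positive values mean too favourable. At 20% leaving, the last two rows reach 0.14 and 0.11. If leaving is unrelated to year-1 change, the bias is about 0. Later leavers do little harm because their Week 16 change from HZN-825 Baseline already carries the year-1 loss.

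**2. Arm contrast under reading A.** Equal selective leaving in each prior arm gives equal biases, which cancel. If one arm loses 10% selectively (0.55) and another 5% at random (0.00), the contrast is off by 0.55 - 0.00 = 0.55.

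**3. Arm contrast under reading B, no dropout.** Assumptions: FVC SD 15, year-1 change SD 5 and independent of the starting value, measurement SD 3, true arm difference 3.0 arising wholly in year 1.

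- Within-arm covariance of two-year change with Trial Baseline: 5² = 25.
- Variance of Trial Baseline: 15² + 5² + 3² = 259.
- Slope: 25/259 = 0.097.
- Adjusted difference: 3.0 - 0.097 × 3.0 = 2.71.

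With year-1 SD 6 the slope is 36/270 = 0.133 and the result 2.60. If only half the difference (1.5) arises in year 1, with SD 5, the result is 3.0 - 0.097 × 1.5 = 2.86. With HZN-825 Baseline as the only covariate, randomised arms have equal expected baselines and the difference stays at 3.0.

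**4. Response or covariate?** Adding the 301 Week 52 FVC to reading A as a second covariate leaves the first row of the table unchanged, since subjects without a response still drop out. Adding the 301 Week 52 change as a response brings the bias to at most 0.02 in every scenario.

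**The case against.** A reader might infer that the protocol's FVC model is wrong or omits the 301 Week 52 value. It does not: Protocol 9.6.3 concerns change from Trial Baseline, and that value is its covariate. The gap lies in one SAP sentence, and even there the omission is inferred. The phrase about post-Trial Baseline visits could, by analogy, be taken to cover all visits after HZN-825 Baseline, including 301 visits. SAP 7.4 leaves window details to the table shells, which are not available here. What the text itself shows is under-specification.

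A reader might also infer that those who stop for lack of efficacy are lost. Protocol 9.3.3.1 says "Discontinuation of trial drug due to lack of efficacy is at the discretion of the Investigator or subject", but goes on to keep such subjects in the trial for assessments through Week 52 unless they withdraw for another reason. Those who leave are asked back for the Week 52 assessments, which include spirometry, and SAP 7.4 maps every observation to a visit. This stands: the larger biases need leaving before Week 16 with no discontinuation FVC. It is not a full answer, because return is requested and cannot be assured.

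A bias of about one point is also tempting to quote. In this simulation it needs 20% leaving before Week 16, strongly selectively and without later spirometry (1.07). Nothing in the documents supports that.

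Finally, SAP 9 plans no formal inference, and observed summaries are given as well. That limits the consequence but does not settle which model is to be run.

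**Conclusion.** The point holds as a gap in SAP 9.1. The model for half of the primary endpoint is not fixed, and each plain way of completing it has an avoidable defect.

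- **HZN-825 Baseline as covariate:** the two-year mean is too favourable by about 0.15 to 0.3 points at 5% leaving and 0.3 to 0.55 at 10%, but only if year-1 decliners selectively leave before Week 16 without discontinuation spirometry. Otherwise the bias is about 0.14 or less. The arm contrast is biased by dropout only if selective leaving differs by prior arm, so a general claim that dropout shrinks the contrast is not supported.
- **Trial Baseline as covariate:** a year-1 arm difference of 3.0 becomes about 2.7 under the assumed SDs, with no dropout at all.

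The directions follow from the model structure; the sizes rest on the assumed SDs, dropout rates and selectivity. The effect is on a descriptive estimate, with no formal test or error rate involved. The change is worth making because it is cheap and uses data already held.

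**What to change.** In SAP 9.1, replace the one-sentence reference by a written-out MMRM for change from HZN-825 Baseline:

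- **Responses:** change at 301 Week 52 (the Trial Baseline visit) and at 302 Weeks 16, 28, 40 and 52.
- **FVC covariate:** HZN-825 Baseline only.
- **Unchanged:** stratification factors, prior treatment, visit, prior treatment by visit, and unstructured covariance.

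State how discontinuation spirometry enters the model, and report how many full analysis set subjects have no 302 FVC after Day 1, with their year-1 change. Use the same form, with each measure's own scheduled visits, for the exploratory MMRMs of change from HZN-825 Baseline. Leave the Trial Baseline model as it is.

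The cost is SAP wording and one more response row per subject. The covariance matrix grows from 4×4 to 5×5, that is from 4×5/2 = 10 to 5×6/2 = 15 parameters, so the existing non-convergence fallback should be kept. No new data are needed. The change does not address which 301 subjects chose to enter 302.
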